## 11.0 SPECIMEN COLLECTION AND BANKING

Urine, saliva, and blood samples will be collected and analyzed at the SCTR Research Nexus Laboratory, Clinical Neurobiology Lab at MUSC Institute of Psychiatry or an external lab. Unused/unanalyzed saliva, blood plasma, and urine samples will be stored at the SCTR Research Nexus Laboratory and maintained for future, undesignated research. Only the PI will have permission to request sample retrieval for IRB-approved research on which the PI is a principal or co-investigator. Only de-identified data will be shared along with these samples. Samples will not be used for genetic analysis. Participants can request to withdraw samples from banking by contacting Research Staff or the PI.

## 12.0 DATA MANAGEMENT

### **Specific Aim: Evaluate the associations between cognition, stress, endogenous progesterone, cannabis use, and biomarkers of ADRD risk, and whether sex plays a moderating role.**

Consistent with the CUD literature in adulthood (Sagar & Gruber, 2018), we hypothesize that older adults with CUD will demonstrate normatively worse cognitive function. The primary measure is the Global Cognitive Abilities factor (Kiselica et al., 2020). This is a psychometrically robust, factor analytically-derived (using 12 neurocognitive test scores), and demographically-normed (for age, sex, and years of education) index that yields a z-score representing global cognitive function. We will conduct one-sample t-tests to determine whether this CUD sample's z-score mean is significantly below the normative population mean of z-score=0.

We will conduct preliminary analyses to examine whether this effect is greater in women than in men, hypothetically due to post-menopausal loss of progesterone and greater levels of stress driving cannabis use. The measures of interest are the Global Cognitive Abilities factor z-score, baseline progesterone measurements, and stress (i.e. averaged pre- and post-cue CREMA session data and TSST cortisol and subjective ratings). First, we will conduct independent samples t-tests to determine whether the Global Cognitive Abilities factor z-score is different between sexes. Second, we will run analyses of covariance (covariate: age) to test differences in baseline progesterone between men and post-menopausal women (which should be absent per Oettel & Mukhopadhyay, 2004). Next, we will run Spearman's rank correlations to investigate associations between stress and Global Cognitive Abilities by sex. Should stress be a more salient feature among women with CUD, we would find an inverse correlation between CREMA session data and Global Cognitive Abilities in women.

We will examine the extent to which cognitive decrements are associated with ADRD biomarkers to generate subsequent hypotheses regarding the potential impact of cannabis use on ADRD risk. We will conduct Spearman's rank correlations between the Global Cognitive Abilities factor z-scores and ADRD biomarkers (with transformations, as appropriate), by sex, to obtain preliminary estimates of potential associations between cognition and ADRD risk in the setting of CUD.

**Power and Sample Size.** This is a pilot study for the purposes of generating preliminary data to establish feasibility and power analyses for subsequent grants. The proposed analyses will provide effect sizes with which to generate sample size estimates. It will also provide us preliminary data for the acceptability of "real world" assessment of stress via CREMA in a population for whom proficiency with mobile technologies is diminished. Importantly, with our detailed assessment of menstrual, reproductive, and menopausal history, we will be able to meaningfully characterize hormonal influences on the hypothesized effects among women.

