## 1.0 OBJECTIVES / SPECIFIC AIMS

This study is funded through an administrative supplement to the parent SCORE grant (U54 DA016511, Pro# 00081360; PI: [name]), hereafter referred to as the “parent study.”

The primary objective of this supplement study is to collect pilot data to expand the relevance of Cannabis use disorder (CUD) to Alzheimer’s disease and related dementias (ADRD). We will recruit older adults ages 50-80 with CUD to undergo the proposed assessments in addition to ADRD-focused biomarkers (from MRI, blood, and neurocognitive testing) of ADRD risk.

**Specific Aim: Evaluate the associations between cognition, stress, endogenous progesterone, cannabis use, and biomarkers of ADRD risk, and whether sex plays a moderating role.** Consistent with the CUD literature in adulthood, we hypothesize that older adults with CUD will demonstrate normatively worse cognitive function. We will conduct preliminary analyses to examine whether this effect is greater in women than in men, hypothetically due to post-menopausal loss of progesterone and greater levels of stress driving cannabis use. We will examine the extent to which cognitive decrements are associated with ADRD biomarkers to generate subsequent hypotheses regarding the potential impact of cannabis use on ADRD risk.

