### 3.0 STUDY ENDPOINTS

**Primary Outcome:** Global Cognitive Ability (GCA). Consistent with the CUD literature in adulthood (Sagar & Gruber, 2018), we hypothesize that older adults with CUD will demonstrate normatively worse cognitive function. The primary measure is the GCA factor (Kiselica et al., 2020). This is a psychometrically robust, factor analytically-derived (using 12 neurocognitive test scores), and demographically-normed (for age, sex, and years of education) index that yields a z-score representing global cognitive function.

*Planned analysis:* We will first conduct one-sample t-tests to determine whether this CUD sample's z-score mean is significantly below the normative population mean of z-score=0. We will then statistically test whether GCA is lower in women than in men, hypothetically due to post-menopausal loss of progesterone and greater levels of stress driving cannabis use. Next, we will assess the associations between GCA and progesterone measurements and stress (i.e. averaged pre- and post-cue CREMA session data and TSST cortisol and subjective ratings), by sex. Finally, we will examine the associations between GCA and ADRD biomarkers, by sex, to obtain preliminary estimates of potential associations between cognition and ADRD risk in the setting of CUD.

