## **6.0 NUMBER OF SUBJECTS**

Target completion is 50 participants, comprising men (n=25) and women (n=25).

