Measures: Female participants will be asked to give a saliva sample every morning they complete CREMA. Female participants will be given instructions on how to collect and store a saliva sample on Day 0. They will complete the sample within 30 minutes of waking up and before eating or drinking. All participants will complete the pre- and post-cue subjective measures of craving and stress, obtained as follows. At the start of each CREMA session, participants will be asked to provide ratings on craving, mood, and stress using a modified version of the Within Session Rating Scale (WSRS; Childress et al., 1986). This visual analog scale is anchored with adjectival modifiers. The scale includes items assessing anxiety, stress, irritability, and craving. If the session is one of the two daily picture assessments, next a photograph (either stress-related or neutral) will be presented and the participant will be instructed to look at it carefully for 10 seconds. Each picture cue will appear only once during the study. An alarm will sound at the end of each trial, after which participants will complete a post-cue WSRS assessment, ratings of how carefully they looked at the photographs and their distraction level during each trial, and data on their cannabis use since last assessment. If the session is only collecting ambient stress and craving, immediately after the WSRS the participants will be asked to record data on cannabis use since the last assessment session.

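### The aim asks whether sex moderates the associations, but for stress and cognition section 12.0 plans only by-sex correlations, with no contrast between the sexes

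*Combined protocol and SAP*

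**What the plan says.** The Specific Aim, in section 1.0 and again in section 12.0, is to evaluate the associations between cognition, stress, progesterone, cannabis use and dementia-risk biomarkers, "and whether sex plays a moderating role". A worse cognitive result in women is put down, tentatively, to "post-menopausal loss of progesterone and greater levels of stress driving cannabis use".

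Section 12.0 plans these steps that involve sex:

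- Independent-samples t-tests "to determine whether the Global Cognitive Abilities factor z-score is different between sexes".
- An age-adjusted analysis of covariance of baseline progesterone in men and post-menopausal women, with no difference expected.
- Spearman "rank correlations to investigate associations between stress and Global Cognitive Abilities by sex". The reading attached to this step is that, if stress is more prominent among women with cannabis use disorder, "we would find an inverse correlation between CREMA session data and Global Cognitive Abilities in women".
- Spearman correlations of GCA with the dementia biomarkers, by sex.

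Section 3.0 covers the same ground. It defines stress as "averaged pre- and post-cue CREMA session data and TSST cortisol and subjective ratings), by sex", adds GCA-progesterone associations by sex, and names no test for any of these associations. Neither section plans a contrast between the women's and men's correlations, or a comparison of stress levels between the sexes. Section 6.0 sets the target at 25 men and 25 women. The power paragraph in section 12.0 describes a pilot whose analyses are to supply effect sizes for later sample-size estimates.

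**The concern.** Moderation of an association by sex means that the association differs between the sexes. The first two steps are direct comparisons, but of means, so they say nothing about an association. The stress-GCA step is the one where the plan makes a comparative statement about women, yet the evidence it names comes from women alone. Equal correlations in both sexes would produce the same finding.

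Two things are at stake. An inverse coefficient in women could be reported as a sex difference without any comparison having been made. And the effect size that a later study of moderation would need, the between-sex difference with its interval, is not among the planned outputs. A smaller gap of the same kind is that greater stress in women is part of the proposed explanation, but stress level is not compared between the sexes.

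**Working it through.** The documents give no alpha, power or expected correlation for this step, so there is no figure of the plan's own to reproduce.

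**Inputs.** n = 25 per sex (section 6.0, assuming complete data). Spearman correlations by sex (section 12.0). Assumed: bivariate normal data, two-sided 0.05, and true correlations from 0 to -0.5.

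**Step 1: the logic.** Women and men are independent samples. The distribution of the women's coefficient depends on the women's true correlation and on n, and not on the men's correlation. A statement about women only therefore has the same probability whether men show the same association or none. This needs no simulation.

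**Step 2: precision of the contrast.** For Spearman coefficients on the Fisher-z scale, SE of the difference = sqrt(2 x 1.06/(n - 3)) = sqrt(2.12/22) = 0.310. The 95% CI half-width is 1.96 x 0.310 = 0.61.

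**Step 3: simulation**, 500,000 pairs of samples per row:

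| True rho, women / men | Women's r below 0 | Women significant, inverse | Women significant, men not | Fisher-z contrast rejects |
|---|---|---|---|---|
| 0 / 0 | 50% | 2.6% | 2.4% | 4.4% |
| -0.3 / -0.3 | 92% | 28% | 20% | 4.7% |
| -0.4 / -0.4 | 97% | 47% | 25% | 4.8% |
| -0.5 / -0.5 | 99% | 68% | 22% | 5.0% |
| -0.3 / 0 | 92% | 28% | 27% | 15% |
| -0.5 / 0 | 99% | 69% | 65% | 39% |

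The fifth column can be checked by hand in the equal-rho rows, since the samples are independent: 0.281 x (1 - 0.281) = 0.202; 0.470 x 0.530 = 0.249; 0.684 x 0.316 = 0.216.

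The third and fourth columns depend only on the women's rho. With women at -0.5 they are significant in 68% of studies when men are also at -0.5, and in 69% when men are at 0; the one-point gap is simulation noise. The contrast moves from 5% to 39%. When women are significant under equal rho of -0.3, -0.4 or -0.5, the 95% CI for the difference still includes zero in 92%, 95% and 96% of studies.

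**Step 4: an example.** Suppose the observed coefficients are -0.5 in women (nominally significant, since the threshold is about 0.40 in absolute value) and -0.2 in men (not significant). The difference on the z scale is -(0.549 - 0.203) = -0.347. Then 0.347/0.310 = 1.12, p = 0.26, and the 95% CI is -0.347 +/- 0.608, or -0.96 to 0.26.

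**Step 5: what 25 per sex cannot do.** By the normal approximation, 80% power for -0.5 against 0 needs 2.12 x (2.80/0.549)^2 + 3, or about 59 per sex.

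**Step 6: stress level.** The 95% CI half-width for a difference in means is t(0.975, 48) x sqrt(2/25) = 2.011 x 0.283 = 0.57 SD.

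**The case against.** The strongest reply is that the sentence is a conditional expectation: if stress matters more among women, a certain pattern would be seen. A reader might infer that the plan will take a significant correlation in women as proof of moderation. The documents do not say that, and they attach no alpha to the step. This stands. The 20-25% figures describe what would happen if someone read the results that way; they are not the error rate of an announced rule. What survives is that the expected pattern does not bear on the comparative premise, and no other planned output does.

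Other stronger readings also fail:

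- *That the plan never compares the sexes, or states expectations for women only throughout.* Mean GCA and progesterone are compared directly, and the progesterone expectation covers both sexes. The gap concerns the associations, and the women-only expectation is confined to the stress-GCA step.
- *That higher mean stress in women is a hypothesis left untested.* The text offers stress driving cannabis use as a tentative mechanism. Comparing stress levels would describe one part of it and would not test whether stress drives use.
- *That the CREMA stress measure is undefined.* Sections 3.0 and 12.0 specify averaged pre- and post-cue data, and section 10.0 names a stress item. Whether other rating items also enter the score is a separate question.

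It can also be said that this is a pilot, that both coefficients will be available so the contrast can be computed afterwards, and that it will rarely be decisive. All true, and this limits the consequence. But a pilot meant to supply effect sizes is the place to plan this estimate, and low precision makes a reading from one sex less safe.

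**Conclusion.** The concern holds in a limited form. For stress and GCA, the plan does not produce the quantity that its moderation aim asks about, and the one interpretive sentence names a pattern that is equally likely whatever the correlation in men. Under equal true correlations of -0.3 to -0.5, a reading based on separate significance would suggest a difference (women significant, men not) in about 20-25% of studies, against about 5% for the direct contrast. Those sizes rest on 25 complete participants per sex, bivariate normality and a two-sided 5% level that the documents do not state; the logical point needs none of these. No data are missing, the analyses are labelled preliminary, and the primary one-sample GCA test is unaffected. A reader should not infer that the study's main result is compromised.

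**What to change.** In section 12.0:

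1. Pre-specify the women-minus-men difference in the CREMA stress-GCA Spearman correlation, on the Fisher-z scale with its 95% CI, as the estimate of moderation. This uses the statistic already planned.
2. Replace the women-only sentence with, for example: *Correlations are reported for both sexes; whether the association is stronger in women is judged from the between-sex difference and its 95% CI.*
3. Report the by-sex correlations of GCA with progesterone, with the TSST (laboratory stress task) measures and with the dementia biomarkers with the same difference and CI, labelled as exploratory estimates.
4. Add a descriptive women-versus-men difference, with 95% CI, in the stress measures already collected, stating that it does not test whether stress drives cannabis use.

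The cost is SAP wording and a few lines of code on data already being collected, with no new visits. The downside is imprecision. Simulated power is about 15% for -0.3 against 0 and 39% for -0.5 against 0, so the contrast is an estimate for planning later studies and not a confirmatory test, and a claim of a sex difference becomes harder to make.

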Measures:	
ADRD MRI-based biomarkers
 
Medial temporal/hippocampal atrophy and leukoaraiosis volume: These metrics will be obtained using established image analysis pipelines in the PI's laboratory. Structural and functional MRI sequences will be acquired to obtain these and other preliminary data for future studies.
 
Health Variables
 
Vitals (blood pressure, pulse, oxygenation rate, height, weight)
 
Total lipid panel (from blood plasma)
 
High-sensitivity C-reactive protein (from blood plasma)
 
ADRD blood-based biomarkers
 
AB40, AB42, pTau-181, Glial fibrillary acidic protein, Neurofilament light: Measurements will be obtained from blood plasma and assayed through the vendor Quanterix which uses Simoa® technology for sensitive biomarker detection.
 
Neurocognitive testing
 
Version 3 of the NACC-UDS neuropsychological battery (Weintraub et al., 2018): This is the 40-minute test battery that produces the scores needed to generate the Global Cognitive Ability factor.
 
NIH Toolbox – Cognition Battery: We will additionally administer this 20-minute computerized battery to obtain complementary data on cognitive functioning for preliminary data/future research.

Procedure:	DAYS 1-7: CREMA
Setting:	At home, with study-issued or own iPhone
Personnel:	Research staff will be available should participants need assistance

Duration: 3-4 minutes per session, 3 sessions per day

Description: The Cue Reactivity Ecological Momentary Assessment (CREMA) is a cue reactivity assessment in which photographic stimuli are presented multiple times per day on a mobile electronic device. Auditory alarms will alert participants to complete three, randomly scheduled CREMA sessions per day (session = 3-4 mins). Alarms will be distributed over a participant-selected 12-hour period, divided into three, 4-hour blocks with a minimum time of 30 minutes between alarms/CREMA sessions.

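### The GCA-biomarker correlations account for age on the GCA side only; an age-partial Spearman coefficient should be reported beside each planned one.

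*Combined protocol and SAP*

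**What the plan says.** The primary measure, Global Cognitive Ability (GCA), is described in sections 3.0 and 12.0 as a "demographically-normed (for age, sex, and years of education) index that yields a z-score". Section 12.0 plans Spearman's "rank correlations between the Global Cognitive Abilities factor z-scores and ADRD biomarkers (with transformations, as appropriate), by sex" and names no covariate. Section 3.0 gives the same analysis without mentioning age: "we will examine the associations between GCA and ADRD biomarkers, by sex, to obtain preliminary estimates".

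Section 10.0 lists two MRI measures ("Medial temporal/hippocampal atrophy and leukoaraiosis volume") and five plasma markers ("AB40, AB42, pTau-181, Glial fibrillary acidic protein, Neurofilament light"). It describes no age norming or adjustment for any of the seven. Inclusion criterion i in section 5.0 admits ages 50 to 80.

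Age is a covariate in one place only, the progesterone comparison in section 12.0: "we will run analyses of covariance (covariate: age").

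Section 6.0 sets the size: "Target completion is 50 participants, comprising men (n=25) and women (n=25"). Each by-sex correlation therefore rests on about 25 people. Under Power and Sample Size, section 12.0 gives the intended use: "The proposed analyses will provide effect sizes with which to generate sample size estimates".

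**The concern.** One variable in each correlation has had age taken out against an external reference, and the other has not. Where a biomarker varies with age over a 30-year range, that variation is noise if GCA carries no age trend. It pulls the coefficient towards zero. If GCA still varies with age in this sample, part of the coefficient reflects shared age, and it can move either way.

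The allowance for transformations does not deal with this, because a monotone transformation of a single biomarker leaves a Spearman coefficient unchanged.

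The effect sizes are a stated product of this pilot. A later study that adjusts for age, but is sized from the unadjusted coefficient, would be planned on a different quantity from the one it will test. A confidence interval on the pilot estimate does not show that mismatch.

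**Working it through.** The plan gives no calculation to reproduce: 50 is a pilot target with no stated alpha, power or effect size.

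**Inputs from the documents.** 25 per sex; 7 biomarkers (2 MRI, 5 plasma); ages 50 to 80; GCA normed for age; no covariate in the GCA-biomarker analysis.

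**Assumed, because the documents give no figure.**
- Age-partial correlation p = -0.40, with biomarkers scored so that higher is worse and rises with age.
- Biomarker variance due to age, R2 = 0.10, 0.25, 0.40, 0.50.
- Residual GCA-age correlation d = 0, -0.2 or +0.2 (and ±0.3 when p = 0).
- Two-sided alpha 0.05 and 80% power for the later study.

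**Formula.** Unadjusted r = p × sqrt((1-R2)(1-d²)) + d × sqrt(R2). With d = 0 this is p × sqrt(1-R2), the semipartial correlation. The formula is exact for linear age adjustment within the sample; with external norms and ranks it is a close approximation.

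**1. Norms remove age (d = 0).** The factors sqrt(1-R2) are 0.949, 0.866, 0.775 and 0.707. The last two columns come from simulation (100,000 runs per cell, uniform age, n=25).

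| R2 | unadjusted r | shift | power, unadjusted | power, age-partial |
|---|---|---|---|---|
| 0.10 | -0.38 | 0.02 | 0.43 | 0.45 |
| 0.25 | -0.35 | 0.05 | 0.36 | 0.44 |
| 0.40 | -0.31 | 0.09 | 0.29 | 0.43 |
| 0.50 | -0.28 | 0.12 | 0.24 | 0.42 |

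On the Spearman scale the simulated means are -0.35 to -0.26 unadjusted and -0.37 to -0.36 age-partial, a shift of about 0.02 to 0.10. With p = 0, both tests reject about 5% of the time.

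**2. A GCA-age trend remains.** In the order of R2 above:
- d = -0.2: r = -0.44, -0.44, -0.43, -0.42 (0.02 to 0.04 too large in size).
- d = +0.2: r = -0.31, -0.24, -0.18, -0.14 (0.09 to 0.26 too small in size).
- p = 0 with d = -0.3 or +0.3: the unadjusted test rejects 0.07, 0.11, 0.14 and 0.17 of the time, the age-partial test about 0.05. These are false positives only with respect to a zero age-partial association.

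**3. Scale against sampling error.** The sampling SD of the coefficient at n=25 is about 0.18 to 0.20 in these scenarios. Of the 12 shifts for p = -0.40, only two exceed it: 0.22 and 0.26, at d = +0.2 with R2 of 0.40 and 0.50.

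**4. Later sample size.** n = 2.802² × (1 + r²/2) / atanh(r)² + 3 + k, rounded up, where (1 + r²/2) is the Spearman variance factor and k = 1 for age-partial, 0 for unadjusted.
- Age-partial, r = 0.40: 7.849 × 1.08 / 0.4236² + 4 = 51.2, so 52.
- Unadjusted, d = 0: 56, 67, 84, 100.
- Unadjusted, d = -0.2: 43, 42, 44, 46. An age-adjusted study of 42 to 46 would have power of about 0.71 to 0.75.
- Unadjusted, d = +0.2: 84, 139, 252, 428.

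For comparison, take sampling error alone in the age-partial estimate at n=25. The standard error is sqrt(1.08/21) = 0.227 on the Fisher scale. The middle half of estimates spans 0.424 ± 0.6745 × 0.227, that is r from 0.26 to 0.52, which implies a later n of 115 down to 31. Nine of the 12 unadjusted values fall inside that range.

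**5. Could the pilot tell which case holds?** A GCA-age correlation of 0.2 is detected at n=25 with power of only about 0.15.

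**The case against.** A reader might infer that the planned correlations are invalid, or confounded by age. The documents do not support that. Section 12.0 seeks preliminary estimates of association and claims no age-independent effect. If the norms work, the unadjusted coefficient is a legitimate estimand with a sound null test, and its only faults are attenuation and lost power. Nothing in the documents shows that a GCA-age trend remains in this sample.

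If one does remain, confounding is one reading. Older users may instead fall further below their norms than younger users, which is close to what the aim sets out to explore. Partialling out age could then remove signal. This objection stands, and it is why the age-partial coefficient should sit beside the planned one and not replace it.

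Nor do the documents say that later studies will adjust for age. A later study that repeats the unadjusted analysis is correctly sized from the unadjusted value. That also stands, and the fix allows for it.

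Finally, the shifts are mostly inside the noise, and with d = 0 a later age-adjusted study would be too large, not underpowered. Both are true and limit the weight of the point. They do not remove the case for a coefficient that needs no new data and recovers power even when the norms are perfect.

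**Conclusion.** The point holds as a modest, inexpensive improvement. The documents establish that age is handled on one side only of the GCA-biomarker analysis and that its effect sizes are meant for later sample sizes. Everything about size rests on assumed values of p, R2 and d.

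With perfect norms, the planned coefficient understates an age-partial -0.40 by 0.02 to 0.12. The power loss is negligible at R2 = 0.10 and substantial at 0.50. A later age-adjusted study would be put at 56 to 100 where 52 is enough. With a residual GCA-age trend the error can go either way, and the documents do not show whether such a trend exists or what it would mean. Age adjustment will not make an estimate from 25 people precise; it makes clear which quantity is being carried forward.

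**What to change.** In section 12.0, add that for each GCA-biomarker pair, within each sex, a Spearman correlation partialled for age will be reported with its 95% CI beside the planned unadjusted one. State that this is done whatever GCA-age correlation is observed, since the sample is too small to guide that choice. Under Power and Sample Size, state that a later study should be sized from the coefficient matching its own analysis: age-partial if it will adjust for age, unadjusted if it will not.

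The cost is wording only, since age is already needed for the GCA norms and the progesterone analysis. One degree of freedom is used per sex: at r = -0.40 and n=25 the 95% CI (Fisher z with the Spearman variance factor) goes from -0.70 to 0.01, to -0.70 to 0.02. The tables grow from 14 coefficients (7 × 2) to 28. The planned analysis is kept in full.
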